The most direct preliminary evidence from our laboratory for the aims of the research in this application is provided by a series of experiments that have been published in *Biological Psychiatry* (33), *Journal of Abnormal Psychology* (86), and *Psychophysiology* (58). This preliminary research that used the startle response to examine the effects of nicotine deprivation has documented comparable affective response among nicotine deprived and non-deprived smokers during brief, unpleasant events and punctate, imminent, cued threats. For example, nicotine deprivation did not increase startle potentiation during brief presentation of unpleasant relative to neutral photographic images (86) [see also (87)]. With respect to potent, punctate certain threats (i.e., cue contingent electric shock), nicotine deprivation did not increase startle potentiation during predictable electric shock administration in two experiments (33,58). Thus, nicotine deprivation following chronic tobacco use does not appear to alter phasic "fear" potentiation of the startle reflex during certain threats. However, these latter two reports offered intriguing evidence that nicotine deprivation may increase negative affective response during uncertain threat. Specifically, nicotine deprivation did increase startle potentiation in the period between threat cues when the smokers are likely anticipating the onset of the next cue at some uncertain time in the near future (58). Furthermore, deprived smokers displayed greater overall startle response than non-deprived smokers during unpredictable shock administration (33). In addition, startle response during unpredictable shock co-varied with smokers self-report of withdrawal symptoms, and was independently predicted by earlier initiation of tobacco use and years of daily cigarette use (33).

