In summary, following smokers during the first two weeks of a smoking cessation attempt provides important laboratory-to-clinical translational benefits. The use of a two week surrogate endpoint for measuring cessation outcomes is innovative and also resource efficient. The use of EMA to track smoking as well as stressor-smoking, stressor-affect and stressor-urge relationships is also innovative in the combination with laboratory measures. These data will allow us to directly examine if 1) our laboratory measures of negative affective response to stressors predict individual differences in stressor coupling with negative affect, urge, and smoking (AIM 2), 2) our laboratory measures predict smoking cessation outcomes across all smokers, regardless of medication group (AIM 3), 3) our laboratory measures differentially predict smoking cessation outcomes across combo NRT vs. placebo as would be expected if combo NRT reduces the influence of negative affect on smoking (AIM 4). To further evaluate AIM 4, we will also re-administer our laboratory cued threat task at 2 weeks post-quit to determine if combo NRT alters negative affective response to stressors and to test if this laboratory measure obtained during treatment mediates combo NRT effects (relative to placebo NRT with counseling) on smoking cessation outcome.

SPECIFIC AIMS

Neuroscience research with animal models implicates neuroadaptation in the stress response as a critical mechanism in the etiology of addiction across multiple classes of drugs including nicotine (22–24). Repeated homeostatic adjustments in the brain's stress systems due to chronic drug administration eventually lead to persistent compensatory adaptations in the structures involved in emotional response and its regulation. Among smokers, these stress neuroadaptations result in dysregulated negative affect when nicotine-deprived and provide the strong motivational press for further smoking that manifests as urge and increased risk for relapse (21,25).

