1.1: Nicotine deprived smokers will display selectively increased negative affect measured via startle potentiation during uncertain (vs. certain) threat relative to non-deprived smokers.

AIM 2: Examine the impact of stress neuroadaptation on negative affect, smoking urge, and smoking in response to stressors. Laboratory startle potentiation measures of stress neuroadaptation will predict ecological momentary assessment measures of:

2.1 ...overall levels of negative affect and urge
2.2 ...within-smoker covariation (i.e., coupling) of episodic stressors with negative affect, urge, and smoking (i.e., stressor-induced negative affect, urge and smoking).

AIM 3: Examine the impact of this stress neuroadaptation on smoking during the first two weeks of smoking cessation.

3.1: Laboratory startle potentiation measures of stress neuroadaptation will predict overall smoking during the first two weeks post-quit as well as measures of point prevalence abstinence and continuous abstinence measured at 2 weeks post-quit.

AIM 4: Determine if treatment of withdrawal via NRT reduces the influence of stress neuroadaptation.

4.1: Combo NRT with counseling (vs. placebo NRT with counseling) will reduce startle potentiation measures obtained at one week post-quit.

4.2: The effect of combo NRT (vs. placebo NRT with counseling) on smoking and related outcome measures will be mediated by change in startle potentiation measures from pre-quit to post-quit.

4.3: Treatment of withdrawal symptoms via combo NRT will attenuate the predictive strength of pre-quit startle potentiation measures with respect to overall levels of negative affect, urge, and smoking and stressor-induced negative affect, urge, and smoking.

RESEARCH DESIGN AND METHODS

C1: BRIEF OVERVIEW

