All participants report some demographic information, their current affective state (Positive and Negative Affect Scales-PANAS (120), provide information on a broad-band personality measure (Brief Multidimensional Personality Questionnaire- bMPQ); (121) and supplemental measures of trait affectivity relevant to individual differences in anxiety including the Intolerance of Uncertainty Inventory, (122), and the Anxiety Sensitivity Inventory (123). Individual differences in depressive symptoms will also be recorded Center for Epidemiologic Studies Depression Scale Revised (CESD-R; 125) and the Depression Anxiety Stress Scale-21 (DASS-21).

These measures are available to serve as covariates to increase power to test for focal effects on relevant outcome measures. They are also available as possible individual difference moderators in supplemental analyses. After completing the self-report measures, participants schedule their first experimental session. Participants are randomized to either a nicotine deprived or non-deprived condition and instructed to abstain from all nicotine containing products for 24 hours prior to their nicotine deprived session or to continue their normal pattern of smoking prior to their non-deprived session.

Finally, participants receive brief cessation counselling, schedule their experimental visits and quit date, and are provided with verbal and written instructions about the 3-week daily EMA survey that begins one week before their quit date.

C2.3: Laboratory Experimental Session(s)

All participants complete the cued threat task (NPU; see section C3 below) in each of two separate experimental sessions. Their first session is either nicotine deprived and non-deprived in a counterbalanced order, the final is 2 weeks post-quit. The deprived group completes their first experimental session the day after the start of their quit attempt, and the non-deprived group completes it before the start of their quit attempt. Data across the two experimental sessions will be used to provide sensitive within-subjects tests of deprivation effects on startle potentiation measures of stress neuroadaptation (Aim 1) and to address all subsequent Aims (2-4).

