Analysis of Treatment Outcome (AIMS 3, 4.1, 4.2): Number of cigarettes smoked (17,18), point prevalence abstinence and continuous abstinence (as defined by the SRNT Workgroup on Biochemical Confirmation (149)) will be analyzed in Generalized Linear Models with time (1 week vs. 2 weeks) as a within subject factor. Startle potentiation measures from the cued threat task will be included as quantitative regressors to test if our laboratory stress neuroadaptation biomarkers predict treatment outcome measures (Aim 3). As above, treatment condition can be included as a moderating between subject factor to test if the relationships between startle potentiation and treatment outcome differ generally when withdrawal symptoms. Finally, mediation analyses can be conducted to determine if NRT alters startle potentiation measures at one-week post quit (AIM 4.1) and the startle potentiation measures mediate NRT effects on smoking outcome measures (AIM 4.2).

C4.3: Sample Size Justification. The primary analyses of startle potentiation will be accomplished within the General Linear Model (GLM). The analyses of smokers test for a two way interaction between Deprivation Status and Threat Uncertainty. Cohen (150) defines 0.15 for the squared multiple partial correlation as a medium effect size for GLM analyses. To be conservative, we powered our experiments to provide 90% power to detect a somewhat smaller (0.10) effect size. N=142 will provide 90% power to detect a squared multiple partial correlation of 0.10 for the interaction in a model that contains the two main effects and interaction based on formula provided by Cohen. We then increased this sample size to the round 150 within each Treatment Group to provide flexibility to counterbalance all relevant additional task factors. This yields N=300 across the two Treatment Groups. Given that the multilevel models that will be used to test questions about the EMA data are essentially GLMs fit at two separate levels of analysis (occasion and person levels), N=150 within each Treatment Group will provide comparable high power to test person-level predictors of both occasion-level intercepts (e.g., overall smoking, levels of negative affect) and stressor coefficients (e.g., stress-instigated smoking or negative affect).

DATA AND RECORD KEEPING

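### The Aim 3 models do not commit to adjusting the startle coefficient for baseline smoking or smoking history, so they can test prediction but cannot separate startle from smoking history for the impact claim

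*Combined protocol and SAP*

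**What the plan says.** All references are to the combined protocol and SAP.

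- **Aim 3 (Specific Aims).** The aim is to "Examine the impact of this stress neuroadaptation on smoking during the first two weeks of smoking cessation". Hypothesis 3.1 beneath it is worded as prediction of post-quit smoking and abstinence. Section A5 sets the scope as whether "our laboratory measures predict smoking cessation outcomes across all smokers, regardless of medication group".
- **Analysis of Treatment Outcome (Aims 3, 4.1, 4.2).** Cigarettes smoked, point prevalence abstinence and continuous abstinence "will be analyzed in Generalized Linear Models with time (1 week vs. 2 weeks) as a within subject factor". Then: "Startle potentiation measures from the cued threat task will be included as quantitative regressors". The next sentence adds that "treatment condition can be included as a moderating between subject factor". No baseline smoking, smoking-history or dependence term is named.
- **Section A3.** In the laboratory's earlier work, "startle response during unpredictable shock co-varied with smokers self-report of withdrawal symptoms", and that startle response "was independently predicted by earlier initiation of tobacco use and years of daily cigarette use". No coefficient is given.
- **Section C2.2.** FTND, WISDM and a Smoking History Questionnaire are collected at screening. Of the screening measures the plan says: "These measures are available to serve as covariates to increase power to test for focal effects on relevant outcome measures".
- **Aim 1 and EMA analysis sections.** Level of dependence appears only as a possible exploratory moderator.
- **Section C2.5.** One pre-quit week of EMA records cigarettes smoked, four reports a day.

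**The concern.** Participants are randomised to NRT or placebo, and to deprivation status at the first session. They are not randomised to a level of startle potentiation. The Aim 3 startle coefficient is therefore an observational association.

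Under the plan's own theory, chronic smoking produces the neuroadaptation, so smoking history comes before startle. If a longer or earlier history also makes quitting harder by any other route, history is a common cause of startle and of post-quit smoking. A model with only time and startle would then credit part of the history effect to the biomarker.

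What is at stake is the reading of a positive result. Aim 3 speaks of impact, and section A5 says the two-week outcome is meant to establish that the laboratory measure is clinically important. A positive unadjusted coefficient would leave open whether startle says anything that the screening questionnaires do not already say.

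The second cost is precision. Treatment arm is expected to affect the outcome, since section A5 describes NRT as roughly doubling long-term abstinence. Pre-quit smoking is a natural baseline for post-quit smoking. Neither is committed to the model.

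**Working it through.** **The plan's own figure.** No sample size or power is stated for Aim 3. The only calculation in the plan (N=142 for 90% power, Aim 1 interaction) can be recovered with alpha assumed at 0.05, three numerator degrees of freedom and 0.10 read as f²: 14.17/0.10 = 141.7, or 142. It does not bear on this point.

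**Is adjustment committed anywhere?**

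| Place | Role given to dependence or history | Binding for Aim 3? |
|---|---|---|
| Analysis of Treatment Outcome | None named | No |
| C2.2 | Available covariates, for power | Optional; no model or variable named |
| Analysis of Startle Potentiation (Aim 1) | Exploratory moderator | Different model |
| Analysis of EMA (Aims 2, 4.3) | Exploratory moderator | Different model |

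A moderator analysis asks whether the startle slope differs by dependence. That is not adjustment of the slope.

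**How large could the effect be?** The documents give no correlation between startle and history or dependence, nor between dependence and post-quit smoking. Everything below is assumed:

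- startle-dependence correlation a = 0.1, 0.2, 0.3;
- dependence-smoking correlation b = 0.2, 0.3, 0.4;
- startle has no effect of its own;
- N=300 with complete data, linear outcome, two-sided 5% test.

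Induced correlation: r = a × b. Rejection probability by Fisher's z: with d = atanh(r) × √(N−3), P = 1 − Φ(1.96 − d) + Φ(−1.96 − d).

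Worked case, a=0.2 and b=0.3: r = 0.06; d = 0.0601 × √297 = 0.0601 × 17.23 = 1.035; P = 1 − Φ(0.925) + Φ(−2.995) = 0.178 + 0.001 = 0.179.

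| a \ b | 0.2 | 0.3 | 0.4 |
|---|---|---|---|
| 0.1 | 6.4% | 8.1% | 10.6% |
| 0.2 | 10.6% | 17.9% | 28.2% |
| 0.3 | 17.9% | 34.3% | 54.7% |

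A simulation (2,000 trials per case, linear outcome, N=300) agrees. Without dependence in the model, the startle test rejected in 18% (a=0.2, b=0.3), 34% (0.3, 0.3) and 56% (0.3, 0.4) of trials. With dependence in the model it rejected in 4% to 5%.

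**Precision.** If pre-quit cigarettes per day correlates 0.3 to 0.5 with the post-quit outcome (assumed), adjustment removes 0.3² = 9% to 0.5² = 25% of outcome variance in a linear model. This is only the assumption squared.

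**Where the pre-quit week may be used.** The EMA models cover all three weeks, and the first of these is the pre-quit week. Pre-quit EMA cigarettes per day would there be part of the smoking outcome. It is a legitimate covariate only when the outcome is post-quit.

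**The case against.** The strongest reply is that hypothesis 3.1 claims prediction, and an unadjusted coefficient is the direct test of prediction. That stands. A reader might infer from the table that 18%, or even 55%, is the false-positive rate of hypothesis 3.1. It is not: an induced correlation of 0.06 is a genuine non-zero association. The rates apply only to the further claim that startle has an effect of its own.

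Second, the plan regards neuroadaptation as a driver of further smoking. FTND and cigarettes per day may therefore be partly its consequences, and adjusting for them can remove some of the effect under study. This also stands. It argues for showing both estimates, and against treating the adjusted one as the only valid answer. It has less force for age at initiation and years of daily smoking, which the theory places upstream.

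Third, the evidence in section A3 is indirect. It concerns startle response during unpredictable shock, whereas Aim 3 uses potentiation, the threat minus no-threat difference defined in section C3.2. It relates startle to smoking history, not to a dependence score. The entry criteria in section C2.1 (at least 10 cigarettes a day, at least two years, smoking within 30 minutes of waking) may also narrow the range of dependence and favour the lower figures. The link is a credible warning, not a measured bias.

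Fourth, the plan describes its analyses as general strategies and leaves screening covariates available, so it would be wrong to infer that adjustment is excluded. But an optional covariate with no named model leaves the choice until results are known.

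**Conclusion.** The concern holds in limited form. The Aim 3 specification commits to time and startle, with treatment as an optional moderator, and nothing in the document commits to adjusting a non-randomised predictor for baseline smoking or smoking history. A positive result would support the statement that startle predicts post-quit smoking. It would not support the statement that startle matters beyond smoking history or dependence, which is where the word impact in Aim 3 leads.

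The size cannot be derived from the documents. The range of about 6% to 55%, with 18% at correlations of 0.2 and 0.3, is arithmetically sound but rests wholly on assumed correlations, a linear outcome and 300 complete cases. Two of the three outcomes are binary.

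Two further inferences are not supported. A reader might conclude that the Aim 3 estimate is known to be biased; the documents show a plausible route, not an amount. A reader might also hold that leaving out covariates pulls the logistic abstinence coefficient toward zero. That is a difference between marginal and conditional odds ratios rather than confounding bias, and it forms no part of this point.

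**What to change.** In the Analysis of Treatment Outcome section, for post-quit outcomes:

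1. Include treatment arm as a main effect and pre-quit cigarettes per day as a covariate.
2. Prespecify an adjusted model that adds age at initiation, years of daily smoking and FTND.
3. Report its startle coefficient beside the unadjusted one from the time-and-startle model.
4. State which claim each supports. Plain prediction may cite the unadjusted coefficient; any statement that startle matters beyond smoking history or dependence should cite the adjusted one.
5. Do not add pre-quit EMA cigarettes per day to the three-week EMA models.

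The cost is a few sentences. FTND, smoking history and the pre-quit EMA week are already collected, and arm is known. The document does not list the items of the Smoking History Questionnaire, so confirm that it records age at initiation and years of daily smoking. The downside is that the adjusted estimate may be smaller because dependence may lie partly on the causal path, which is why both coefficients should be shown.

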These EMA data are collected to evaluate the relationships between individual differences in psychophysiological affective response in our cued threat task (overall and deprived vs. non-deprived negative affect generally and fear/anxiety selectively) and real time, *in vivo*, affective response, smoking urge, and cigarette use. We will test if our laboratory-assessed psychophysiological individual differences predict individual variability in affective response, urge, and cigarette use recorded via EMA. We will also examine stress-affect, stress urge, and stress-smoking coupling (i.e., temporal covariation over 2 weeks post-quit between stressor experience, strength of affective response, and cigarette urge and use). We will also examine if any of these relationships differ across (i.e., are moderated by) Treatment Groups (Combo NRT with counseling vs. placebo NRT with counseling).

C2.5.1: Design Considerations and Justification. The use of EMA methods with 4X daily reports allows for increased precision with respect to temporal ordering of stressors, affect, smoking urge, and cigarette use. The survey was kept brief to decrease assessment burden. Similar (and longer) length surveys have been completed with high compliance (> 80% response rates) in Drs. [name] and [name]'s research with community smokers. We acknowledge that these reports are subjective based on the participants' individual appraisal of stressor severity and their own affective response to these stressors. However, these individual differences are at the core of our predictions regarding increased negative affective response across stressors among smokers, particularly when nicotine deprived. We predict that our laboratory measures will identify the smokers who will show consistently strong negative affect generally and in response to aversive stressors, and that these smokers will have poorer smoking cessation outcomes.

C2.6: Post-Quit Laboratory Visit

We will measure treatment adherence, additional treatment/medication usage, stressors, affective status, withdrawal, urge, and cigarette use for smokers at a follow-up laboratory visit at 2 weeks post-quit. This visit will also allow for biological confirmation of smoking status via CO measurement (CO < 6ppm).

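### The startle predictor for Aims 2 and 3 is not tied to a session, and two sections bring the 2-week session into it

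*Combined protocol and SAP*

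**What the plan says.** **Text that brings in both sessions**

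- Section C2.3 gives each smoker two sessions and says of their timing that "the final is 2 weeks post-quit". The first session is deprived for some smokers and non-deprived for others. "The deprived group completes their first experimental session the day after the start of their quit attempt", while the non-deprived group has it before quitting. The same paragraph sends data from the two sessions to tests of "startle potentiation measures of stress neuroadaptation (Aim 1) and to address all subsequent Aims (2-4".
- Section C2.5 describes the laboratory predictors of EMA outcomes as "overall and deprived vs. non-deprived negative affect generally and fear/anxiety selectively".

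**Text that names no session**

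- Aim 3.1: "Laboratory startle potentiation measures of stress neuroadaptation will predict overall smoking during the first two weeks post-quit", together with abstinence at 2 weeks.
- Analysis of Treatment Outcome, for Aim 3: "Startle potentiation measures from the cued threat task will be included as quantitative regressors".
- The EMA analysis section, for Aim 2, uses startle as a person-level predictor over all three EMA weeks.

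**Text that points to the early session only**

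- Section A5: "To further evaluate AIM 4, we will also re-administer our laboratory cued threat task at 2 weeks post-quit".
- Section C2.6 gives two purposes for the 2-week task: testing medication effects on startle, and mediation.
- Aim 4.3 limits its predictor to pre-quit startle.

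The Aim 1 analysis text still refers to two pre-quit sessions, which the schedule in C1, C2.3 and C3 does not contain.

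**The concern.** Aims 2 and 3 claim prediction: startle measured in the laboratory should forecast affect, urge and smoking during the quit attempt. That claim needs the predictor to come before the outcome and to be free of its influence.

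The 2-week session meets neither condition. It falls at the end of the EMA and smoking window, after two weeks of assigned treatment. On the plan's own thesis (Aim 1.1), nicotine deprivation raises startle to uncertain threat, so whether a smoker has abstained or relapsed would itself move 2-week startle. Abstainers would tend to score higher because they are abstinent. That produces an association of high startle with less smoking, the opposite of what section C2.5.1 expects, namely poorer cessation among strong responders. Mixed into the predictor, it could create an association where none exists, or offset a real one. In either case it could not be called prediction.

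**Working it through.** **1. Which sessions can supply each predictor**

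Under the current schedule a smoker has one early session, deprived or non-deprived, and one session at 2 weeks. A deprived versus non-deprived difference within a smoker needs two sessions in different states. With only one early session, the second must be the 2-week session. So the C2.5 predictor and the C2.3 sentence both lead to 2-week data for Aims 2 and 3, and the two analysis sections contain nothing that stops this. A5, C2.6 and Aim 4.3 point the other way.

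**2. Order in time**

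| Measure | Timing |
|---|---|
| Pre-quit EMA | the week before quit day |
| First session, non-deprived group | before quit day |
| First session, deprived group | day after the quit attempt starts |
| Post-quit EMA and cigarette counts | the two weeks after quit day |
| CO-confirmed abstinence | the 2-week visit |
| Second session | the same 2-week visit |

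The second session is therefore at or after the end of the EMA smoking record and concurrent with CO-confirmed abstinence.

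The first session is not clean for every outcome either. In the deprived group it follows the whole pre-quit EMA week, which is 4 × 7 = 28 of the 4 × 21 = 84 scheduled reports. It also requires 24 hours without tobacco and CO below 6 ppm.

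**3. Size**

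The plan gives no figure for this point. Its N of 142 concerns the Aim 1 interaction, and nothing here depends on it. The two calculations below assume no true prediction (first-session startle unrelated to smoking), N = 300 from the plan, and a two-sided 5% level, which is assumed because the plan states no alpha.

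*Model A, continuous smoking.* Assumed: between-session correlation 0.5; smoking shifts 2-week startle by *b* SD per SD. The mean of the two sessions has covariance *b*/2 with smoking and variance (1 + 1 + 2 × 0.5)/4 = 0.75, so r = (*b*/2)/√0.75 = 0.577*b*. Rejection rates from 5,000 simulated trials:

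| b | r of two-session mean | Two-session mean | 2-week startle alone | First session alone |
|---|---|---|---|---|
| 0 | 0 | 5% | 5% | 5% |
| 0.1 | 0.058 | 18% | 41% | 5% |
| 0.2 | 0.115 | 51% | 94% | 5% |
| 0.3 | 0.173 | 85% | 100% | 5% |

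*Model B, abstinent or not.* Assumed: 35% abstinent; between-session correlation 0.4-0.6; abstainers' 2-week startle higher by d. Borrowing the plan's 0.10 as a squared partial correlation gives d = 2√(0.10/0.90) = 0.67; taking 0.05 instead gives 0.46. For the two-session mean the gap is d/2 and the within-group SD is √((1 + ρ)/2), that is 0.837 at ρ = 0.4 and 0.894 at ρ = 0.6. With d = 0.67 the standardised gap is 0.40 to 0.37. With r = gap × √(0.35 × 0.65)/√(1 + 0.35 × 0.65 × gap²), r is 0.19 to 0.18. Simulated rejection rates for the mean (2,000 replicates):

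| d | Full shift in both arms | Half shift in NRT arm | No shift in NRT arm |
|---|---|---|---|
| 0.67 | 87-91% | 65-70% | 33-37% |
| 0.46 | 57-61% | 35-40% | 18-20% |

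First-session startle alone stays at 4-5%. Non-central t calculations from these correlations agree with the simulated rates: 17%, 52% and 86% in Model A; 86-91% in the first cell of Model B.

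Both models report only rejection when nothing is predicted. Neither measures power lost or sign reversal when a true effect exists.

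**The case against.** The best reply is that the plan means one early predictor throughout. Aim 4.3 says pre-quit, and the EMA section tests Aim 4.3 by adding treatment to the Aim 2 models, so the same predictor is natural there. A5 and C2.6 describe the 2-week task in Aim 4 terms. The C2.3 sentence can be read as each session serving its own aims. The contrast in C2.5 may be left over from a design with two pre-quit sessions, as the Aim 1 analysis text suggests. The analysis section also presents itself as exemplars of analysis options, not a closed specification.

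Much of this stands. Three stronger inferences are tempting, and the documents do not support them:

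- *That 2-week startle does enter the Aim 3 model.* No passage says so. C2.3 and C2.5 lead there and the analysis sections do not prevent it, while other sections point away.
- *That all outcome data precede the second session.* CO-confirmed abstinence is taken at the same visit.
- *That a rejection rate near 90% is the expected error.* No passage proposes averaging sessions. The abstinence rate and between-session correlation are assumed. The 0.10 is a power target for a Deprivation by Threat Uncertainty interaction, not a gap between abstainers and relapsers at two weeks. The top figures also assume that NRT leaves the shift intact, contrary to what Aim 4.1 expects.

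The reply does not remove the conflict. C2.3 is the section that sets the current schedule, and its sentence covers Aims 2-4 without distinction. A5 and C2.6 do not confine the 2-week task to Aim 4. If the C2.5 contrast is a leftover, it still has to be withdrawn, because it cannot be built from the early session.

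**Conclusion.** The point holds as an internal conflict with a biased result on one of its readings. Followed as written, C2.3 and C2.5 allow the Aim 2 and 3 predictor to include startle taken at the end of the outcome window, after treatment, and plausibly altered by the outcome.

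The size cannot be fixed from the documents. For a two-session mean at N = 300, assumed shifts of 0.1-0.3 SD per SD, or gaps of 0.46-0.67 SD with varying NRT suppression, give roughly 18-90% rejection with nothing to predict. First-session startle gives about 5% throughout, and if smoking does not move 2-week startle there is no inflation. The direction implied by the plan's thesis is opposite to its hypothesis, so masking is as much a risk as a false finding. A reader might infer that a true effect would be reversed; that has not been shown.

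**What to change.** - In the EMA and Treatment Outcome analysis sections, state that Aims 2, 3 and 4.3 use first-session startle only.
- Put first-session deprivation condition (deprived or non-deprived) in those models as a covariate and, if wanted, as a moderator, because the measure is taken in different states in the two groups.
- Treat as predicted only EMA and smoking data collected after the first session. Report relations with earlier EMA data as associations.
- Reserve 2-week startle for Aims 4.1 and 4.2.
- Reconcile C2.3, C2.5, the two pre-quit sessions in the Aim 1 analysis text, and the pre-quit wording of Aim 4.3 with the current schedule. Pre-quit alone does not describe the deprived group's first session. Aim 4.1, C2.4.1 and the Treatment Outcome section also place the on-treatment task at one week, where C1, C2.3 and C2.6 place it at two.

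This changes text and model specification, not data collection. The costs are a less reliable predictor than two sessions would give, and no within-person deprivation-change predictor for Aims 2 and 3. It does not settle Aim 4.2, where startle measured after the smoking window is the proposed mediator of smoking; that needs its own justification.
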